8.5.4.2 Adverse event summaries by SOC, PT and grade

The number and percentage of subjects reporting unsolicited AEs occurring up to 28 days post each dose and regardless of the number of doses will be summarized by PT nested within SOC and by grade. AEs with a missing grade will be presented in the summary table with a grade category of "Missing".

Similar analyses will be provided for:

- SAEs (from Day1 through Visit 14)
- SAEs related to IMP (from Day1 through Visit 14)
- AEs related to IMP (from Day 1 through 28 days post each dose and regardless of the number of doses)
- Solicited AEs that continue longer than 7 d post-dose or are a SAE (from Day 1 through 28 days post each dose and regardless of the number of doses)
- MAAEs (from Day 1 through 28 days after each dose)
- Non-serious AEs (from Day 1 through 28 days post each dose and regardless of the number of doses)
- AEs leading to study withdrawal (any such AEs reported during the study)
- AEs leading to IMP discontinuation (any such AEs reported during the study)

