8.5.4 Adverse events

All AEs will be recorded from Visit 1 (Dose 1) until 28 days after each dose; only unsolicited AEs starting after the first IMP administration will be collected. SAEs will be collected from date of informed consent and throughout the whole trial (i.e., until Visit 14). Medically attended adverse events (MAAE) will be collected until 28 d after each dose.

Solicited AEs (i.e., reactogenicity events) are recorded in the trial subjects' e-diaries and should not be reported as AEs unless the solicited AE meets criteria for an SAE or continue past Day 7 of each IMP dose.

Page 23 of 36 Version: 3.0 Date: 08 MAY 2024

All AEs will be coded using the most recent version of MedDRA® coding system version 25.1 or later and graded for severity using FDA Guidance for Industry: "Toxicity Grading Scale for Healthy Adult and Adolescent Volunteers Enrolled in Preventive Vaccine Clinical Trials"⁴. In case a subject has an AE with missing relationship status, the event will be assumed to be related. No imputation for missing grades will be performed.

If an AE is reported more than once by the same subject for a System Organ Class (SOC) / Preferred Term (PT) the associated AE will be counted once for the SOC / PT under the maximum severity.

All AE summary tables will be sorted alphabetically by SOC and PT within SOC.

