8.5.4.1 Overall summary of adverse events

The number and percentage of subjects reporting the below events will be summarized for the subjects in safety set.

- Unsolicited AEs with onset from Day1 through Day 28 post IMP dose will be summarized for each dose (i.e., 1st dose, 2nd dose, 3rd dose) and regardless of the number of doses received. All events entered on the "Adverse Events" eCRF page with an onset date within the above-mentioned timeframe will be analysed. This includes solicited events that persisted beyond Day 7 after IMP administration or that qualified as an SAE. The following will be analysed:
 - Any unsolicited AEs
 - Related AEs
 - AE of grade >=3
 - Related AEs of grade >=3
 - Any solicited reactogenicity event that continues longer than 7 d post-IMP administration or is an SAE
 - Unsolicited AEs leading to withdrawal of IMP
 - Unsolicited AEs leading to study withdrawal
 - SAEs, with onset from Day 1 through Visit 14. The following will be analysed:
 - Any SAEs
 - Related SAEs
 - SAEs of grade >=3
 - Related SAEs of grade >=3
 - MAAE, with onset from Day1 through 28 days after each dose. The following will be analysed:
 - Any MAAEs
 - Related MAAEs

Page 24 of 36 Version: 3.0 Date: 08 MAY 2024

- MAAEs of grade >=3
- Related MAAEs of grade >=3

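### The AE overview counts withdrawals due to AEs only for onsets within 28 days of a dose, the by-term table counts them over the whole study, and the two can disagree, mainly because of SAEs.

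*SAP*

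**What the plan says.** SAP 8.5.4.1 (overall summary) opens its first block with an onset window: "Unsolicited AEs with onset from Day1 through Day 28 post IMP dose will be summarized for each dose". The same block is also shown across all doses. The selection rule is then made explicit, in that only events on the adverse event "eCRF page with an onset date within the above-mentioned timeframe will be analysed". The rows "Unsolicited AEs leading to withdrawal of IMP" and "Unsolicited AEs leading to study withdrawal" follow in that block, and neither has a window of its own.

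The SAE part of the overview has a separate, longer window: "SAEs, with onset from Day 1 through Visit 14. The following will be analysed". Its rows are any, related, grade 3 or higher, and related grade 3 or higher. It has no withdrawal row.

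SAP 8.5.4.2 (by SOC, PT and grade) defines the corresponding tables over the whole study: "AEs leading to study withdrawal (any such AEs reported during the study" and "AEs leading to IMP discontinuation (any such AEs reported during the study".

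On collection, SAP 8.5.4 says "All AEs will be recorded from Visit 1 (Dose 1) until 28 days after each dose". The same section, and protocol 8.3.1, continue SAE collection to Visit 14.

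**The concern.** One quantity, the number of subjects whose AE led to stopping vaccination or leaving the trial, is given two time windows in adjacent sections. A programmer who follows the text would apply two different filters. A reader of the report could then find an overview row lower than the table meant to break it down by term, with no explanation.

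The protocol leaves room for such cases. The criteria for permanent discontinuation of trial treatment in protocol 7.1.3 include possibly related immune-related AEs and set no limit on time since dosing. Protocol 8.5.1 calls for evaluation of possible myocarditis or pericarditis up to 6 weeks after a dose, which is 42 − 28 = 14 days beyond the overview window. A case of this kind that met SAE criteria and began five weeks after Dose 1 or Dose 2 would enter the by-term discontinuation table and not the overview withdrawal row.

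What is at stake is the accuracy of a tolerability count in a summary table and its agreement with the other tables.

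**Working it through.** The plan states no figure for withdrawals, so there is nothing of its own to reproduce. The check compares the two onset windows and then asks which events can fall between them.

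**Inputs**
- Doses on Days 1, 57 and 183 (SAP 3.2).
- Visit 14 at 365 days after Dose 3 (schedule of activities), so nominal Day 183 + 365 = 548.
- Overview window: Day 1 through Day 28 after each dose (SAP 8.5.4.1), with the dose day as Day 1 (SAP 8.1.1).
- By-term window: whole study (SAP 8.5.4.2).
- 16 vaccine recipients per cohort (SAP 3.2). Percentages for AEs use the number in the analysis set (SAP 8.1).

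**Step 1: days covered by the overview window**
- Days 1–28, 57–84 and 183–210: 3 × 28 = 84 days.
- Days not covered: 29–56 (28 days), 85–182 (98 days) and 211–548 (338 days). The sum is 464, and 84 + 464 = 548.
- If the window is read as dose day plus 28, it covers 3 × 29 = 87 days and leaves 461. The difference is immaterial.

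**Step 2: direction**

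Every event inside the 28-day windows is also inside the whole-study window. Hence overview count ≤ by-term count, with equality when no qualifying event starts outside the windows.

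**Step 3: which events can make the counts differ**

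| Onset | Event type | Planned to be collected? | Overview withdrawal row | By-term table |
|---|---|---|---|---|
| Within 28 days of a dose | Any AE | Yes | Counted | Counted |
| Outside those windows | Non-serious AE | No | Not counted | Counted only if recorded anyway |
| Outside those windows | SAE | Yes, to Visit 14 | Not counted | Counted |

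The difference therefore arises mainly in the last line. For IMP withdrawal only onsets before Dose 3 matter (Days 29–56 and 85–182). For study withdrawal Days 211–548 matter too.

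**Step 4: example**

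An SAE with onset on Day 120 prevents Dose 3. Day 120 lies in the 85–182 gap. The by-term table for IMP discontinuation counts 1 and the overview row counts 0.

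**Step 5: size per subject**

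1 / 16 = 6.25 percentage points in a vaccine arm.

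The overview rows say unsolicited AEs, while the by-term rows say AEs. This adds little, because 8.5.4.1 already brings in solicited events that persisted past Day 7 or were serious.

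**The case against.** The strongest reply is that the mismatch is small and hides nothing. Planned collection outside the 28-day windows is confined to SAEs. A disagreement thus needs an SAE that starts there and also leads to withdrawal, or a non-serious AE recorded outside its planned period. In healthy volunteers with 16 vaccinees per cohort this should be uncommon. Such an SAE still appears in the overview's own SAE rows, which run to Visit 14, and only its link to withdrawal is missing there. The link is shown in the 8.5.4.2 tables and the 8.5.4.4 listings. SAP 8.2 tabulates treatment and trial discontinuation with primary reasons, and SAP 8.5.1 tabulates why Dose 2 or Dose 3 was not given. Withdrawal due to AEs is not one of the primary estimands, and the AE estimand itself uses 28 days after each dose. The planned escalation review follows the 7-day follow-up after Dose 1 and uses all available data, so this row does not drive it.

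All of that stands, and it limits the point to a minor one. It does not reconcile the two definitions.

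A reader might also infer that the overview misses about two thirds of the withdrawals that could stop a later dose, since 126 of the 182 days before Dose 3 (69%), or 124 of 182 (68%) with dose day plus 28, lie outside its windows. The documents do not support this. It is a share of calendar time, and non-serious AEs are not routinely collected on those days, so it says nothing about the share of countable events.

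**Conclusion.** The inconsistency is real and minor. As written, the overview withdrawal rows can be too low and can disagree with the by-term tables. The disagreement is 6.25 points for each affected subject in a 16-subject arm, and zero if no qualifying event starts outside the windows. The documents give no basis for estimating how often that will happen. No data are lost, and no primary estimand or planned escalation decision changes.

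This rests on two assumptions. The two withdrawal rows are taken to belong to the 28-day block, as their position before the SAE entry and the absence of any window of their own indicate. The whole-study wording in 8.5.4.2 is taken as deliberate, which is likely because other entries in that list state a 28-day window and these two do not.

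**What to change.** In SAP 8.5.4.1, for the summary regardless of the number of doses, define the two withdrawal rows as any such AE reported during the study, matching 8.5.4.2. If per-dose cells are kept for these rows, label them as counts of events with onset within 28 days of that dose.

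The cost is a line or two of SAP text, one extra table label and one programming condition. The small downside is that the per-dose cells may not add up to the across-doses count, and the label should make the reason clear. No change to data collection is needed.

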8.5.4.3 Adverse event summaries by SOC and PT

The number and percentage of subjects reporting the following events will be tabulated by SOC and PT, regardless of the grade:

- SAEs occurring from Day 1 through Visit 14
- Non-serious AEs occurring up to 28 days post each dose and regardless of the number of doses.

8.5.4.4 AE listings

All deaths, AEs, SAEs, MAAEs, AEs leading to withdrawal of IMP, AEs leading to study withdrawal and AEs leading to death will be presented. Solicited AEs will be flagged in all AE listings.

8.5.5 Laboratory assessments

Hematology, clinical chemistry, urinalysis, Follicle stimulating hormone (FSH) and pregnancy tests will be performed by a local laboratory.

For the purposes of summarizing and presentation in tables and listings, all laboratory values will be presented in System International (SI) units. If a laboratory value is reported

Statistical Analysis Plan (SAP) BNT165-01

BioNTech SE Confidential Page 25 of 36 Version: 3.0 Date: 08 MAY 2024

using a nonnumeric qualifier e.g., less than (<) a certain value, or greater than (>) a certain value, the given numeric value will be used in the summary statistics, ignoring the nonnumeric qualifier.

Absolute values of clinical laboratory variables at each protocol scheduled visit and its change from baseline will be summarized using descriptive summary statistics for each parameter listed in the protocol.

Categorical variables will be summarized using number and percentage.

Shift tables from baseline to each visit will be presented. Shifts will be done based upon grading from FDA guidance for industry 'Toxicity Grading Scale for Healthy Adult and Adolescent Volunteers Enrolled in Preventive Vaccine Clinical trials'.

Abnormal and clinically significant, abnormal and not clinically significant and normal laboratory values will be summarized for each parameter by visit.

All laboratory data will be presented in the data listings and abnormal clinical laboratory values will be flagged in the listing. Laboratory values that are below or above the normal reference ranges will be flagged.

The results of FSH, pregnancy test and Urinalysis (Dipstick and Microscopy tests) results will be listed only.

8.5.6 Vital signs

Vital sign parameters to be summarized include systolic and diastolic blood pressure, heart rate, respiratory rate and oral body temperature. Body temperature will be presented in Celsius (°C).

Absolute values for vital sign parameters at each visit and change from baseline to each post-baseline visit will be summarized using descriptive summary statistics for each parameter. Note that vital signs will be collected both pre- and post-IMP administration.

Abnormal clinically significant, abnormal not clinically significant, and normal values of will be listed only.

8.5.7 12-Lead electrocardiogram (ECG)

Absolute values of heart rate collected at each time-point, and its change from baseline to each post-baseline time-point will be summarized using descriptive summary statistics for the subjects in safety set.

In addition, the investigators evaluation at each visit (Normal, Abnormal – not clinically significant and Abnormal – clinically significant) will be tabulated by visit.

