Record concomitant medication since last visit		Х	х	х		Х	х	х	Х		х	х	х		х	х	х	х
Blood draws for humoral response assessments h		X f 30 mL					X f 30 mL		X 30 mL		X 30 mL	X f 30 mL	X 30 mL		X 30 mL	X 30 mL	X 30 mL	X 30 mL
CCI																		
Blood draw for genetics		X ^f 4 mL																

Page 10 of 82 Version: 4.0 Date: 13 FEB 2023

Activity	Visit (V) 0	V 1	V 2	V 3	VS1 (Call)	V 4 (Call)	V 5	V 6	V 7	V S 2 (Call) ^p	V 8	V 9	V 10	VS3 (Call) P	V 11	V 12	V 13	V 14
Visit description	Screen ing	Dose (D) 1 (Day 1)	1 d FU post- D 1	7 d FU post- D 1	(14 d post- D 1)	28 d FU post- D 1	D 2 (Day 5 7)	1 d FU post- D 2	7 d FU post- D 2	(14 d post- D 2)	28 d FU post- D 2	D 3 (Day 1 83)	7 d FU post- D 3	(14 d post- D 3)	28 d FU post- D 3	84 d FU post- D 3	168 d FU post-D 3	365 d FU post-D 3 or ET
Visit window	-30 to -	N/A	±4 h	+2 d	+1 d	±2 d	±2 d	±4 h	+2 d	+1 d	±2 d	±7 d	+2 d	+1 d	±2 d	±10 d	±10 d	±10 d
CCI																		
Subject hotline availability	Start	=>	=>	=>		=>	=>	=>	=>		=>	=>	=>		=>	=>	=>	End
Issue, train and collect subject e-diaries		Issue, train ⁱ					Re- train ⁱ					Re- train ⁱ	Collect					
Subjects report reactogenicity (incl. oral body temperature) daily for 7 d after each IMP dose using an e-diary		Start after Dose 1	=>	End ⁿ			Start after Dose 2	=>	End ⁿ			Start after Dose 3	End ⁿ					
Investigators review e-diary data daily		Start	=>	End			Start	=>	End			Start	End					
Record AEs, MAAEs, and SAEs ^j		х	х	х		Х	х	х	х		х	х	х		х	х	х	х
Wellbeing phone call		X k			X۰		X k			Χ°		X k		Χ°				
Investigator local reaction assessment		Χ¹					Χ¹					Χ¹						

Page 11 of 82
Version: 4.0
Date: 13 FEB 2023

Activity	Visit (V) 0	V 1	V 2	V 3	VS1 (Call)	V 4 (Call)	V 5	V 6	V 7	V S 2 (Call) ^p	V 8	V 9	V 10	V S 3 (Call) ^p	V 11	V 12	V 13	V 14
Visit description	Screen ing	Dose (D) 1 (Day 1)	1 d FU post- D 1	7 d FU post- D 1	(14 d post- D 1)	28 d FU post- D 1	D 2 (Day 5 7)	1 d FU post- D 2	7 d FU post- D 2	(14 d post- D 2)	28 d FU post- D 2	D 3 (Day 1 83)	7 d FU post- D 3	(14 d post- D 3)	28 d FU post- D 3	84 d FU post- D 3	168 d FU post-D 3	365 d FU post-D 3 or ET
Visit window	-30 to - 1 d	N/A	±4 h	+2 d	+1 d	±2 d	±2 d	±4 h	+2 d	+1 d	±2 d	±7 d	+2 d	+1 d	±2 d	±10 d	±10 d	±10 d
Cumulative blood volume (mL)	20	164	10	70		0	150	10	160		140	155	155		140	140	140	140

- a Brief (symptom-orientated) physical examination.
- b Before (up to 1 h) dosing and at 1 h (±15 minutes) after dosing.

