8 STATISTICAL ANALYSES

8.1 General considerations

In general, all summaries will be displayed by individual vaccine DL and combined placebo. A total group, combining all subjects on placebo and active vaccine, will be presented in addition for accounting (subject disposition), demographics and other baseline characteristics and protocol deviations as applicable unless otherwise specified.

No formal statistical comparisons between vaccine DL of BNT165b1 and placebo will be performed. Missing data, other than that described for partial or missing dates for AEs/concomitant medications/vaccinations (as described below) will not be imputed.

Continuous variables will be summarized using the following descriptive statistics: number of subjects with non-missing data (n), mean, SD, median, minimum (min) and maximum (max).

Categorical variables will be summarized by absolute and relative frequencies (n and %) of subjects in each category and the number of subjects with missing data ('missing' category will be presented if there is one or more missing value).

For event-driven occurrence data (e.g., adverse event, concomitant medication, etc.) percentages will be based on the number of subjects in the analysis set (N). For reported visit data (e.g., lab etc.) percentages will be based on the number of subjects with non-missing values (n).

The rates of binary endpoints such as safety variables (systemic and local reactions) will be provided.

Page 13 of 36 Version: 3.0 Date: 08 MAY 2024

All data collected during the trial will be listed based on safety set unless otherwise specified. The trial day will be presented as appropriate. Listings will be sorted by dose level, site number, subject number, and date of assessment or date of onset (if applicable).

All trial data will be presented at the visit as assigned in the Case Report Form (CRF). No windowing of data for the purposes of assigning to a visit will occur. Unscheduled assessments will not be included in summaries/analysis but will be included in the listings.

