8.1.1 General definitions

Baseline is defined as last available value prior to first dose of trial IMP.

Generally, if there are multiple pre-baseline assessments available for a particular day, the assessment that is closest to the day (and time if collected) of the first dose of a trial treatment will be used as the baseline value.

Change from baseline: Unless otherwise specified, this will be calculated as follows:

Change from baseline = post-baseline assessment value – baseline assessment value.

If either the baseline or post-baseline assessment value is missing, the change from baseline is set to missing as well.

Body mass index (BMI) will be calculated as follows:

BMI
$$\left(\frac{\text{kg}}{\text{m}^2}\right) = \frac{\text{Weight (kg)}}{\text{Height(m)}^2}$$

Temperatures collected in °F will be converted to °C as follows:

$$^{\circ}C = (^{\circ}F - 32) * 5/9$$

Duration will be calculated as follows:

• Duration = last observation date - first observation date + 1.

For conversion of days to months or years the following rules will be applied:

- 1 month = 30.4375 days
- 1 year = 365.25 days

Trial Day will be calculated as follows:

- If assessment/onset date < date of first IMP dose, then trial day = assessment date
 date of first IMP dose
- If assessment/onset date >= date of first IMP dose, then trial day = assessment/onset date - date of first IMP dose + 1

That is, trial day 1 indicates the date of first IMP dose.

The day relative to dose 2 or dose 3 will be calculated as follows:

Statistical Analysis Plan (SAP)

BNT165-01

Page 14 of 36

Version: 3.0

Date: 08 MAY 2024

 If assessment/onset >= date of second IMP dose and < date of third IMP dose, then day relative to dose 2 = assessment/onset date - date of second IMP dose + 1

If assessment/onset >= date of third IMP dose, then
 day relative to dose 3 = assessment/onset date – date of third IMP dose + 1

All trial data will be presented at the visit in the visit assigned in the Case Report Form (CRF)/visit assigned in external data. No windowing of data for the purposes of assigning to a visit will occur.

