8.5 Safety analyses

The primary endpoints of this trial include local reactions, systemic events, AEs, SAEs and MAAEs.

Other Safety data that will be summarized includes physical examinations, vital signs, height, body weight, electrocardiogram (ECGs) and clinical safety laboratory assessments (including Hematology and Clinical chemistry). All safety analyses will be based on the safety set and will be summarized by each dose level, combined placebo and visit if applicable.

Page 18 of 36 Version: 3.0 Date: 08 MAY 2024

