8.5.2.2 Acute local reactions

Investigators will assess acute local reactogenicity at the visits given in Section 10.4. Investigators will grade and record acute local reactions as described in Table 4. The number and percentage of subjects reporting acute local reactions (pain at the injection site, erythema/redness, induration/swelling) up to one hour after IMP dose will be summarized by severity and cumulatively regardless of the severity. This summary will include categories "Any", "Grade 1", "Grade 2", "Grade 3" and "Grade 4". The number and percentage of subjects reporting local reactions (pain at the injection site, erythema/redness, induration/swelling) prior to administration of IMP dose will be summarized in a similar manner.

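### At Doses 2 and 3 the SAP takes vital-sign change only from the pre-Dose 1 baseline, with no planned within-subject change from the same-visit pre-dose reading to the 1 h reading

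*SAP*

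**What the plan says.** The schedule of activities (Protocol 1.3, repeated in SAP Appendix 4) gives the timing of vital signs at the three dosing visits, V1, V5 and V9: "Before (up to 1 h) dosing and at 1 h (±15 minutes) after dosing". Protocol 4.2 counts the reading at about 1 h among the safety monitoring that follows each dose.

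SAP 8.5.6 sets the analysis: "Absolute values for vital sign parameters at each visit and change from baseline to each post-baseline visit will be summarized". It then adds: "Note that vital signs will be collected both pre- and post-IMP administration". It does not say how the two readings of a dosing visit are to be related. Values classed as abnormal are to be listed, not tabulated.

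The reference value comes from SAP 8.1.1: "Baseline is defined as last available value prior to first dose of trial IMP". Where several earlier values fall on one day, the one closest to the first dose is used. Change is the later assessment minus this baseline. Protocol 9.4.1 likewise sets a single baseline before the first administration. SAP 8.1.1 also defines a day relative to Dose 2 or Dose 3, but that is a day count and does not create a new baseline.

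**The concern.** The reading at 1 h is there to catch an acute effect of the injection just given. The natural reference is the same subject's reading just before that injection, and the trial collects it at every dose. Under the SAP that pair is never differenced at Doses 2 and 3. The 1 h value is instead compared with one taken before Dose 1. The resulting change carries whatever differs between two visits weeks or months apart, as well as any acute effect.

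What is at stake is how well the report's tables describe acute changes in pulse, blood pressure, respiratory rate and temperature after the second and third injections, where those changes were not recorded as adverse events. Protocol 10.4.1.3.2 does not require every vital-sign abnormality to be recorded as one.

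**Working it through.** **Inputs from the documents.** Doses on Days 1, 57 and 183 (Protocol 6.1). Visit windows of ±2 d for Dose 2 and ±7 d for Dose 3 (Protocol 1.3). Pre-dose reading up to 1 h before dosing, post-dose reading at 1 h ± 15 min. Per cohort, 16 vaccine and 4 placebo subjects, with placebo combined across three cohorts (3 × 4 = 12).

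**Check of the schedule.** 57 − 1 = 56 d, and 56/7 = 8 weeks. 183 − 1 = 182 d, and 182/7 = 26 weeks. Both agree with Week 8 and Week 26 in Protocol 4.1.

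**Age of the reference value, assuming baseline is read on Day 1.**

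| Dose | Planned reference | With visit window | Same-visit reference |
|---|---|---|---|
| 1 | normally the V1 pre-dose reading | – | 0.75 to 2.25 h |
| 2 | 56 d | 54 to 58 d | 0.75 to 2.25 h |
| 3 | 182 d | 175 to 189 d | 0.75 to 2.25 h |

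The shortest same-visit gap is 0 h + 45 min = 0.75 h. The longest is 1 h + 1 h 15 min = 2.25 h.

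**What the longer gap does to the spread.** Take a subject with no reaction. Write each reading as the subject's mean plus a visit effect (SD *sb*) plus a within-visit deviation (SD *sw*), all independent.

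- Change from the pre-Dose 1 value: SD = √(2·sb² + 2·sw²).
- Change within the visit: SD = √2·sw, because the visit effect cancels.
- Ratio of the two: √(1 + (sb/sw)²), which exceeds 1 whenever there is any between-visit variation.

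The documents give no SDs for vital signs. As an illustration only, assume pulse SDs of 4 to 8 bpm for each component:

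| sb | sw | Planned change SD | Same-visit SD | Ratio |
|---|---|---|---|---|
| 4 | 8 | √160 = 12.6 | 11.3 | 1.12 |
| 6 | 6 | √144 = 12.0 | 8.5 | 1.41 |
| 8 | 4 | √160 = 12.6 | 5.7 | 2.24 |

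The direction follows from the algebra. The size depends on the assumed ratio sb/sw.

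**What can be recovered from the planned output.** If both readings are tabulated on the same subjects, the difference of their means is the mean same-visit change. The SD, median and range of that change cannot be obtained from the two separate summaries, because they depend on how the readings pair within subjects. They would have to be computed from the listings.

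**The case against.** The strongest reply is that nothing is contradicted and little is lost. The protocol uses the same single baseline, leaves other safety analyses to the SAP (9.4.4), and never promises a same-visit change. The pre-Dose 1 value is a legitimate reference: it is the only one free of earlier vaccine exposure, and its wider spread belongs to a different quantity. Individual pairs stay visible, since "All data collected during the trial will be listed based on safety set unless otherwise specified". The combined placebo column carries the same between-visit variation, so it largely protects the comparison of means and gives a yardstick for the spread. Vital signs belong to the secondary tier: "Other Safety data that will be summarized includes physical examinations, vital signs, height, body weight". Clinically significant changes become adverse events under Protocol 10.4.1.3.2. All of this stands. It limits the point to an added summary and makes it minor.

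Stronger readings are tempting, and the documents do not support them:

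- *The same-visit change is missing at every dose.* At Dose 1 the baseline is normally the V1 pre-dose reading, so change from baseline to the 1 h reading is the same-visit change. The only doubt is that SAP 8.5.6 speaks of post-baseline visits where the ECG section (8.5.7) speaks of time-points.
- *Presenting data by CRF visit (SAP 8.1) merges or drops one of the two readings.* That rule decides which visit a record belongs to. It says nothing about time points within a visit.
- *The SAP already gives local reactions the paired analysis that vital signs lack.* SAP 8.5.2.2 plans separate summaries, with reactions "prior to administration of IMP dose will be summarized in a similar manner". It plans no within-subject change.
- *The extra spread can be turned into a chance of spurious large rises.* The SAP sets no cut-off or rule for vital-sign change, and every SD would be assumed. Such a figure would describe nothing that the trial tabulates or acts on.

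**Conclusion.** The point holds for Doses 2 and 3. The only planned change for the 1 h reading there uses a reference nominally 56 or 182 days old, although one from at most 2 h 15 min earlier is collected. No SD, median or range of the within-subject same-visit change is planned. At Dose 1 only the wording needs tightening.

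The impact is minor. A reader might infer that safety oversight is weakened, but the documents do not support that. The primary endpoints, pausing rules and Internal Review Committee review do not rest on this table, and no hypothesis is tested. What improves is the precision with which the report describes acute vital-sign change.

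The conclusion rests on the text of SAP 8.1.1 and 8.5.6 and on day arithmetic. The SD illustration is not needed for it.

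**What to change.** In SAP 8.5.6 add:

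*For each dose, change from the same-visit pre-dose reading to the 1 h post-dose reading will be summarized (n, mean, SD, median, min, max) by DL and combined placebo, with values shown by time point (pre-dose, 1 h, 7 d).*

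Keep the change from the pre-Dose 1 baseline, which answers a different question, and keep the listings. Showing values by time point also settles the ambiguity at Dose 1.

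The cost is one sentence and one derived variable from readings already collected. No assessment or visit is added and no planned output is removed.
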